Identification Number	Version Number	State	Effective date
FORM-000050125	2.0, CURRENT	Effective	08, Jan 2021

TEAE	Treatment Emergent Adverse Event	
UNL	Upper Normal Limit	
UPT	Urine Pregnancy Test	
ZOF	Zofenopril	

MENARIN	Corporate Medical Department		
Identification Number	Version Number	State	Effective date
FORM-000050125	2.0, CURRENT	Effective	08, Jan 2021

1 RESPONSIBILITIES

Sponsor:	Name: Menarini International Operations		
	Luxembourg SA		
	Address: [name]		
	[contact]		
	[contact]		
Clinical Trial Coordinator:	Name: [name]		
	Address: [name]		
	[contact]		
	e-mail: [contact]		
Study Medical Expert (SME):	Name: [name]		
	Address: [name]		
	[contact]		
	e-mail: [contact]		
Study Drug Safety Manager (SDSM):	Name: [name]		
	Address: [name]		
	[contact]		
	e-mail: [contact]		
Coordinating Investigator	Name: [name]		
	Address: [name]		
	[contact]		
	e-mail: [contact]		
CRO	Name: Biorasi		
	Address: [name]		
	[name]		
	[contact]		
	e-mail: [contact]		
Statistician	Name [name]		
	Address: Statistician and SAS Programmer,		
	Consultant. Foxhound Analytics LLC		
	[contact]		
	e-mail: [contact]		

МЕМАЯІМІ	Corpo	orate Medical Departme	nt
Identification Number	Version Number	State	Effective date
FORM-000050125	2.0, CURRENT	Effective	08, Jan 2021

[figure not shown]
Protocol Version 1.0 of 1 23/04/2021

PROTOCOL SYNOPSIS 2

Title	Interventional clinical trial to assess efficacy and safety of the extemporaneous combination of zofenopril calcium and amlodipine in grade 1-2 hypertensive patients versus each monotherapy
Acronym Sponsor Study Code	MASOLINO Study MEIN/20/ZoAm-Hyp/001
Study product, Dosage and Regimen: -Investigational Product -Reference Therapy (comparator)	Extemporaneous combination of Zofenopril (ZOF) 30 mg (ATC code: C09AA15) with Amlodipine (AML) 5 mg (ATC code: C08CA01) or Amlodipine (AML) 10 mg (ATC code: C08CA01) will be administered orally once daily.
Study Type and Design	This study is a phase IV, open-label, multicentre, multinational study with two study periods, treating patients with grade 1-2 hypertension, blood pressure (BP) ranging from ≥140/90 mmHg to ≤179/109 mmHg while on treatment with any angiotensin converting enzymeinhibitors (ACE-i) or Calcium Channel Blockers (CCBs) including ZOF 30 mg or AML 5 mg respectively. The study is designed with a run-in period of 4 weeks and an assessment period of 8 weeks.
Phase	Phase IV
Objectives*	Primary Objective: To assess the anti-hypertensive efficacy of the extemporaneous combination of ZOF 30 mg with AML 5 mg or AML 10 mg in lowering the sitting diastolic BP between Visit 2 (Week 0) and Visit 4 (Week 8) in patients with uncontrolled BP

немани		Corporate Medical Department		
		V · V ·	St. 4	T266 (*)
Identificati	on Number	Version Number	State	Effective date
FORM-0	00050125	2.0, CURRENT	Effective	08, Jan 2021

	anning to the start of with 70E (20 mg) on AMI (5 mg) mag athousing				
	previously treated with ZOF (30 mg) or AML (5 mg) monotherapies				
	for at least 4 weeks.				
	Secondary objectives:				
	•To assess the antihypertensive efficacy of the extemporaneous				
	combination of ZOF 30 mg in combination with AML 5 mg or AML				
	10 mg in lowering sitting systolic BP between Visit 2 (Week 0) and				
	Visit 4 (Week 8) in patients with uncontrolled BP previously treated				
	with ZOF 30 mg or AML 5 mg monotherapies for at least 4 weeks.				
	•To assess the antihypertensive efficacy of the extemporaneous				
	combination of ZOF/AML 30/10 mg vs. ZOF/AML 30/5 mg, in				
	lowering sitting DBP and SBP between Visit 3 (Week 4) and Visit 4				
	(Week 8) in patients with uncontrolled BP previously treated with				
	ZOF or AML 5 mg monotherapies for at least 4 weeks.				
	• To evaluate the total number and percentage of patients who				
	achieved the BP goal (sitting BP ≤130/80 mmHg) at Visit 2 (Week				
	0), at Visit 3 (Week 4) and at Visit 4 (Week 8).				
	•To assess the compliance to the treatment (percentage of actual				
	doses taken versus doses to be taken) at Visit 2 (Week 0), at Visit 3				
	(Week 4) and at Visit 4 (Week 8).				
	•To evaluate the safety and tolerability of the monotherapies (ZOF				
	30 mg and AML 5 mg) and of the extemporaneous combinations				
	(ZOF 30 mg and AML 5 mg or AML 10 mg) after 8 weeks of				
	treatment.				
	Primary Efficacy Endpoint:				
Endpoints*	•Change in mean sitting DBP between Visit 2 (Week 0) and Visit 4				
Enupoints	(Week 8).				
	Secondary Efficacy Endpoint:				
	•Change in mean sitting SBP between Visit 2 (Week 0) and Visit 4				
	(Week 8).				

Protocol Version 1.0 of 1 23/04/2021

Study Code: : MEIN/20/ZoAm-Hyp/001

- •Change in mean sitting DBP and SBP between Visit 3 (week4) and 4 (Week 8) in patients on combination of ZOF/AML 30/5 with uncontrolled BP at Visit 3 and up titrated to the extemporaneous combination of ZOF/AML 30/10 mg
- •Number and proportion of patients achieving the BP goal (sitting BP≤130/80 mmHg) at Visit 2 (Week 0), Visit 3 (Week 4) and Visit 4 (Week 8).
- •Adherence to the treatments (% of doses taken/ doses to be taken) at Visit 2 (Week 0), Visit 3 (Week 4) and Visit 4 (Week 8).
- •Safety and tolerability of the monotherapies (ZOF 30 mg and AML 5 mg) and of the extemporaneous combination (ZOF 30 mg and AML 5 mg or AML 10 mg) after eight weeks of treatment.

[figure not shown]
Exploratory Efficacy Endpoint:

- •Change in mean sitting SBP and DBP between Visit 1 (week -4) and Visit 2 (Week 0), visit 3 (Week 4) and Visit 4 (Week 8).:
 - in the group of patients who were on ZOF and AML 5 mg at Visit 1 and started ZOF 30 mg or continued the same therapy AML 5 mg at Visit 1
 - in the group of patients who switched to ZOF 30 mg or AML
 5 mg from any other ACE-i or CCBs at Visit 1
- •Change in mean sitting SBP and DBP for uncontrolled patients at Visit 3 (Week 4), between Visit 2 (Week 0) and Visit 3 (Week 4)
- •Number and proportion of patients achieving the BP goal (sitting BP ≤130/80 mmHg) at Visit 2 (Week 0) and Visit 3 (Week 4):
 - in the group of patients who were on and AML 5 mg at Visit 1(Week -4) and started ZOF 30 mg or continued the same therapy AML 5 mg
 - in the group of patients who switched to ZOF 30 mg or AML
 5 mg from any other ACE-i or CCBs at Visit 1 (Week- 4)
- •Number and proportion of patients divided in subgroup by the hypertension grade, the presence of diabetes and/or of

MENARINI	Corporate Medical Department		
Identification Number	Version Number	State	Effective date
FORM-000050125	2.0, CURRENT	Effective	08, Jan 2021

Sponsor: Menarini International Operations Luxembourg SAProtocol Version 1.0 of 1 23/04/2021Study Code: : MEIN/20/ZoAm-Hyp/001

	hypercholesterolemia achieving the BP goal (sitting BP ≤130/80		
	mmHg) at Visit 2 (Week 0), Visit 3 (Week 4) and Visit 4 (Week 8)		
	o in the group of patients who were on ZOF and AML 5 mg at		
	Visit 1 (Week -4) and continued AML 5 mg and started ZOF		
	30 mg		
	o in the group of patients, who switched to ZOF 30 mg or AML		
	5 mg from any other ACE-i or CCBs at Visit 1 (Week 4)		
	•Male or female, Grade 1-2 uncontrolled hypertensive patients ≥18 and ≤65 years of age		
	•Considering a screening failure and a drop-out rate of 25%, the		
	overall number of patients to be screened is 290.		
	•216 patients are needed to complete the run- in period and start the		
	assessment period to guarantee powered results		
	assessment period to guarantee powered results		
	Inclusion Criteria		
	A patient will be considered eligible for inclusion in the study only if		
Study Population:	all the following criteria are met:		
Subjects	1. Male or female Grade 1-2hypertensive patients: with mean		
characteristics	sitting SBP ≥140 mmHg and ≤179 mmHg and/or mean sitting		
Number of	DBP ≥ 90 mmHg and ≤109 mmHg at Screening, with ≥18		
Subjects	and ≤65 years of age, in monotherapy either with ZOF 30 mg		
	or AML 5 mg, or any other ACE-I or CCBs (Felodipine,		
	isradipine, lacidipine, lercanidipine, nicardipine, nifedipine,		
	and nisoldipine) for at least 1 months before Visit 1		
	(Screening).		
	2. Patients who are able to understand and give written informed		
	consent at Screening		
	3. Patients who are available for the entire trial period and willing		
	to adhere to the protocol requirements		
	4. Ability to take oral medication and willing to adhere to the drug		
	regimen		

Protocol Version 1.0 of 1 23/04/2021

[figure not shown]
Study Code: : MEIN/20/ZoAm-Hyp/001

- 5. Female patients are eligible to participate if not pregnant, or not breastfeeding and must refrain from donating or storing eggs. For females of reproductive potential: use of highly effective contraception (e.g., method of birth control throughout the study period and for 4 weeks after study completion defined as a method which results in a failure rate of less than 1% per year) such as:
 - Combined (estrogen- and progestogen-containing) hormonal contraception associated with inhibition of ovulation (oral, intravaginal, transdermal)
 - Progestogen-only hormonal contraception associated with inhibition of ovulation (oral, injectable, implantable)
 - Intrauterine device (IUD)
 - Intrauterine hormone-releasing system (IUS)
 - Bilateral tubal occlusion
 - Vasectomized partner (performed at least 2 months before screening) (if partner is the sole sexual partner of the trial participant and that the vasectomized partner has received medical assessment of the surgical success)
- 6. A male patient must agree to use contraception during the whole study period and for at least 1 week after the last dose of study treatment and refrain from donating sperms during this period

Exclusion Criteria

Any patient who meets any of the following criteria will not qualify for entry into the study:

1. Known contraindications, presence of not recommended / contraindicated concomitant therapy allergies, or significant history of hypersensitivity to zofenopril, amlodipine, other ACE-

Protocol Version 1.0 of 1 23/04/2021

[figure not shown]
Study Code: : MEIN/20/ZoAm-Hyp/001

inhibitors or dihydropyridines calcium channel blockers, or any related products (including excipients of the formulations as outlined in the Investigator's Brochure [IB]) or), summary of product characteristics (SmPCs) or local package inserts for AML and ZOF

- 2. Patients with serious disorders (in the opinion of the Investigator) which may limit the ability to evaluate the efficacy or safety of the tested medications, including cerebrovascular, cardiovascular, renal, respiratory, hepatic, gastrointestinal, endocrine/ or metabolic, haematological, or oncological, neurological, and psychiatric diseases. The same applies for immunocompromised and/or neutropenic patients
- 3. Patients having a history of the following within the last 6 months: myocardial infarction, unstable angina pectoris, percutaneous coronary intervention, bypass surgery, valve replacement (transcatheter aortic valve implantation, MitraClip), cerebrovascular accident (stroke, heart failure, hypertensive encephalopathy, cerebrovascular accident (stroke), or transient ischemic attack. Patients with who have undergone other surgery that in the in the opinion of the Investigator may limit the ability to evaluate the efficacy or safety of the tested medications.
- 4. Patients with secondary hypertension of any aetiology such as renal diseases, pheochromocytoma, Cushing's syndrome hyperaldosteronism, renovascular disease, thyroid disorders
- 5. Patients with severe heart failure (New York Heart Association classification III-IV), a narrowing of the aortic or bicuspid valve, an obstruction of cardiac outflow (obstructive, hypertrophic cardiomyopathy) or symptomatic coronary disease
- 6. Patients with clinical evidence of renal disease as per the Investigator's judgement (including renovascular occlusive disease, nephrectomy and/or renal transplant, bilateral renal artery stenosis or unilateral renal artery stenosis in a solitary kidney, or severe renal impairment)

	MENARINI	Согра	orate Medical Departme	nt
Identification Number		Version Number	State	Effective date
	FORM-000050125	2.0, CURRENT	Effective	08, Jan 2021

	7. Patients with history of angioneurotic oedema			
	8. Patients with clinically relevant hepatic impairment			
	9. Patients with sick sinus syndrome, including sino-atrial block			
	10. Patients with second- or third-degree heart block (without a pacemaker)			
	11. Participation in any other interventional drug trial or exposure to other investigational agents within 30 days before Screening (Visit 1)			
	12. Inability to cooperate or any condition that, in the opinion of the Investigator, could increase the patient's risk of participating in the study or confound the outcome of the study			
	13. Patients with conditions that, in the opinion of the Investigator, would prevent a careful adherence to the protocol			
	14. Patients with severe hypotension			
	15. Patients who suffer from shock (including cardiogenic shock)			
	16. Patients treated with Amlodipine 10 mg and Zofenopril (other than 30 mg)			
Clinical Sites Number of Centres	Approximately 28 clinical sites			
List of Countries	Russia, Hungary, Italy			
Study Duration	• Screening Visit 1, (Week -4)			
(specify different	• Run-in period from Visit 1(Week -4) to Visit 2 (Week 0)			
study phases):	• Assessment period from Visit 2 (Week 0) to Visit 4 (Week 8):			
	The overall duration of the study will be 12 weeks.			
	Screening Visit 1, (Week -4): Grade 1-2 hypertensive patients with			
Subject Study	blood pressure [BP] ranging from ≥140/90 mmHg to ≤179/109			
Phases Duration	mmHg) in treatment with any ACE-i or CCBs*, including ZOF 30			
	mg or AML 5 mg (only dosage allowed) for at least one month prior			
	to Visit 1 will be screened for eligibility.			
	Run-in period from Visit 1(Week -4) to Visit 2 (Week 0): eligible			
	patients will enter a 4 weeks run-in period on the same day of the			

Protocol Version 1.0 of 1 23/04/2021

Study Code: : MEIN/20/ZoAm-Hyp/001

screening visit. Patients previously receiving ZOF 30 mg or AML 5 mg will continue the same treatment, patients receiving other ACE-i will be switched to ZOF 30 mg, while patients receiving CCBs will receive AML 5 mg. Patients entering this phase in therapy with ZOF 30 mg or AML 5 mg should be in a 1:1 ratio. Assessment period from Visit 2 (Week 0) to Visit 4 (Week 8): patients having uncontrolled BP at Visit 2, will be assigned to the extemporaneous combination of ZOF 30 mg and AML 5 mg. After 4 Weeks \pm 2 days the BP will be assessed again (Visit 3): controlled patients (SBP/DBP ≤ 130/80 mmHg) will continue the same extemporaneous combination, while uncontrolled (SBP/DBP >130/80 mmHg) patients will be up-titrated from extemporaneous combination ZOF/AML 30/5 mg to extemporaneous combination of ZOF/AML 30/10 mg for further 4 weeks \pm 2 days (Visit 4, Week 8). At Visit 2 and Visit 3 patients with SBP/DBP value classified as Grade 3 (SBP \geq 180 or DBP \geq 110 mmHg) hypertension will be withdrawn from the study. *To be enrolled in the study, patients could be in monotherapy with one of the listed CCBs: felodipine, isradipine, lacidipine, lercanidipine, nicardipine, nifedipine, and nisoldipine. The primary endpoint will be assessed before and after assessment period at Week 8, by a paired t-test using the Intention-to-treat (ITT) Statistical population and the Per-Protocol (PP) population. Assumptions All the other continuous secondary/exploratory endpoints will be assessed before (Week 0) and after treatment (at Week 8) by a paired t-test. All secondary/exploratory endpoints related to proportion of patients achieving the BP goal at Week 4 and Week 8 will be analysed descriptively producing also the relative 95% CI to assess if there is a significant difference from Week 0 where all patients were uncontrolled.

[figure not shown]
немъни	Corporate Medical Department		
Identification Number	Version Number	State	Effective date
FORM-000050125	2.0, CURRENT	Effective	08, Jan 2021

Protocol Version 1.0 of 1 23/04/2021

Study Code: : MEIN/20/ZoAm-Hyp/001

A total sample size of 216 patients is required to achieve 90% power at a 5% significance level assuming a difference in mean DBP from baseline (Visit 2) to 8 weeks (Visit 4) of 4 mmHg and a standard deviation (SD) for this difference of 10 mmHg. The mean change in DBP for the null hypothesis is set equal to 2 mmHg.

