Participants with uncontrolled BP (>130/80 mmHg) will be provided with ZOF 30 mg and AML 5 mg while participants with controlled BP (≤130/80 mmHg) will be withdrawn from the study

Each trial participant is provided with one treatment Patient Kit made up by

- ZOF 30 mg: one labelled box (white label) containing 42 film-coated tablets (3 blisters with 14 film coated tablets each) of zofenopril calcium 30 mg
- AML 5 mg: one labelled box (white label) containing 42 tablets (3 blisters with 14 tablets each) of amlodipine 5 mg.

The two white labelled boxes are then sealed together into a transparent plastic film to realize the treatment Patient Kit.

Trial participant must be carefully instructed by Investigator to take simultaneously (at the same time): ZOF 30 mg (zofenopril calcium 30 mg) as one oblong film-coated tablet and AML 5 mg (amlodipine 5 mg) as one round tablet, according to Study Protocol.

Visit 3 (Assessment)

Participants with controlled BP (≤130/80 mmHg) are provided with one treatment kit made up by:

- ZOF 30 mg: one labelled box (white label) containing 42 film-coated tablets (3 blisters with 14 film coated tablets each) of zofenopril calcium 30 mg
- AML 5 mg: one labelled box (white label) containing 42 tablets (3 blisters with 14 tablets each) of amlodipine 5 mg.

The two white labelled boxes are then sealed together into a transparent plastic film to realize the treatment kit.

Trial participant must be carefully instructed by Investigator to take simultaneously (at the same time): ZOF 30 mg (zofenopril calcium 30 mg) as one oblong film-coated tablet and AML 5 mg (amlodipine 5 mg) as one round tablet, according to Study Protocol.

Participants with SBP/DBP values classified as Grade 3 hypertension will be withdrawn from the study

Participants with uncontrolled BP (>130/80 mmHg) are provided with one treatment Patient Kit made up by:

иемани	Согр	porate Medical Departm	ent
Identification Number	Version Number	State	Effective date
FORM-000050125	2.0, CURRENT	Effective	08, Jan 2021

- o ZOF 30 mg: one labelled box (green label) containing 42 film-coated tablets (3 blisters with 14 film coated tablets each) of zofenopril calcium 30 mg
- o AML 10 mg: one labelled box (green label) containing 42 tablets (3 blisters with 14 tablets each) of amlodipine 10 mg.

The two green labelled boxes are then sealed together into a transparent plastic film to identify the treatment Patient Kit.

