12.3 Analysis Populations

A total of three populations will be used for all summaries and analyses. Study participants who have satisfied the population criteria will be classified in the designated population and will only be included in analyses for which they have available data.

Data analysis will be performed using the following analysis sets.

The Safety Population

The Safety population is defined as all study participants who sign the informed consent, meet all screening criteria, are enrolled, and receive at least one dose of the assigned treatment during the run-in period. This population will be used for safety analyses.

The Efficacy Population

The Efficacy population is defined as all study participants in the Safety population who complete the 4-week run-in period and the Visit 2 blood pressure assessment. This will be population for efficacy analysis.

The Per-Protocol Population

The Per-Protocol (PP) population is defined as all study participants in the Efficacy population who were dosed according to protocol, complete the required study visits, and do not experience any major protocol deviations that may impact the primary efficacy assessment through end of treatment.

HEVARIN	Corporate Medical Department		
Identification Number	Version Number	State	Effective date
FORM-000050125	2.0, CURRENT	Effective	08, Jan 2021

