### 5.3.3 Efficacy Population (EFF)

The Efficacy Population (EFF) is defined as all study participants in the Safety Population who complete the 4-week run-in period and meet continuation criteria at Visit 2 [uncontrolled BP (sitting SBP/DBP > 130/80 mmHg), tolerate treatment, and fall within 80-120% treatment adherence] and have at least one available post baseline primary efficacy assessment (from Visit 3 or 4). This population will be used for efficacy analyses.

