### 7.1 Efficacy Variable Derivations

### 7.1.1 Blood Pressure (BP) Goal (Controlled v Uncontrolled)

Multiple endpoints (2.3, 3.3, and 3.4) involve patients meeting the BP goal of sitting  $BP \le 130/80$  mmHg at Visit 2 (Week 0), Visit 3 (Week 4) and Visit 4 (Week 8).

A patient will be considered to have met the BP goal (controlled BP) if their SBP  $\leq$  130 mmHg AND their DBP  $\leq$  80 mmHg. If a patient meets one of these criteria but not the other, then they will not be considered to have met the BP goal. That is, a patient's BP is considered uncontrolled if their SBP > 130 mmHg OR their DBP > 80 mmHg.

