### 7.3.2 Proportion of Patients (Endpoints 2.3 and 2.4)

**Endpoint 2.3**: Monotherapy: Number and proportion of patients achieving the BP goal (sitting BP $\leq$ 130/80 mmHg) at Visit 2 (Week 0). Combination therapy: number and proportion of patients achieving the BP goal (sitting BP $\leq$ 130/80 mmHg) at Visit 3 (Week 4) and Visit 4 (Week 8).

**Endpoint 2.4**: Adherence to the treatments (% of doses taken/doses to be taken) at Visit 2 (Week 0), Visit 3 (Week 4) and Visit 4 (Week 8).

Endpoints 2.3 and 2.4 will be analyzed using a 95% binomial confidence interval (CI) for each visit.

A patient who has taken at least 80% and no more than 120% of the required study medication since the last visit will be considered as compliant. Treatment adherence will be summarized incrementally rather than cumulatively so that changes in adherence over time can be accurately reflected. That is, a patient can be compliant between Visits 2 and 3, but non-compliant between Visits 3 and 4, or vice versa.

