# Table 14.2.3.3Proportion of Patients Achieving Sitting BP Goal ( $\leq$ 130/80 mmHg) at Visits 2, 3, and 4(Full Analysis Set and Efficacy Population)

			All Patients
Therapy Type	Visit	Statistic [1,2,3]	(N=xx)
Monotherapy	Visit 2	n/N (Proportion %)	xx/xx (xx.x)
		95% CI	(xx.x, xx.x)
Combined Therapy	Visit 3	n/N (Proportion %)	xx/xx (xx.x)
		95% CI	(xx.x, xx.x)
	Visit 4	n/N (Proportion %)	xx/xx (xx.x)
		95% CI	(xx.x, xx.x)

Note: The Monotherapy analysis (Visit 2) is performed on the Full Analysis Set. The Combined Therapy analysis (Visits 3 and 4) are performed on the Efficacy Population.

[1] A patient is considered to have met the Blood Pressure (BP) goal (controlled BP) if their SBP  $\leq$  130 mmHg AND their DBP  $\leq$  80 mmHg.

[2] n = number of patients who have achieved sitting BP goal at that visit. N = number of patients with data at that visit, regardless of BP goal status.

[3] CI = Confidence Interval.

Source: Listing 16.2.6

Program Name: XXXX.SAS

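### The synopsis reads the Week 4 and Week 8 BP-goal rates as a significance test against a Week 0 rate that is 0% by selection, so a positive result need not reflect any effect of the combination

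*Protocol*

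**What the plan says.** The statistical assumptions in the Protocol synopsis cover all secondary and exploratory BP-goal proportions at Week 4 and Week 8. They call the analysis descriptive and, in the same sentence, add a "95% CI to assess if there is a significant difference from Week 0 where all patients were uncontrolled".

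The goal requires both SBP ≤130 and DBP ≤80 mmHg. Under SAP 7.1.1 "a patient's BP is considered uncontrolled if their SBP > 130 mmHg" or if DBP exceeds 80. Protocol 7.1 gives the combination at Visit 2 to uncontrolled participants, "while participants with controlled BP (≤130/80 mmHg) will be withdrawn from the study"; Protocol 5 and 10 repeat the rule. SAP 5.3.3 builds it into the Efficacy population, whose members must "meet continuation criteria at Visit 2 [uncontrolled BP (sitting SBP/DBP > 130/80 mmHg". The Protocol 12.3 definition is looser, covering those "who complete the 4-week run-in period and the Visit 2 blood pressure assessment". The patients followed to Visits 3 and 4 are the same under either definition, because controlled patients have already left.

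The detailed sections contain no comparison with Week 0. Protocol 12.5.4 specifies a 95% binomial interval per visit, and SAP 7.3.2 says "Endpoints 2.3 and 2.4 will be analyzed using a 95% binomial confidence interval (CI) for each visit". Table 14.2.3.3 prints n/N, percentage and CI, with no p-value and no difference. No document names the CI method. SAP section 10, which lists departures from the Protocol, does not mention the synopsis clause.

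**The concern.** Nobody who continues past Visit 2 can be at goal at Week 0, so the rate can only stay at 0 or rise. A reference of exactly 0% is refuted by a single patient at goal, whatever put that patient there. The study is non-randomised and has no parallel control, so nothing in the design shows how many patients uncontrolled at one visit would measure below 130/80 at the next without added treatment.

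The detailed sections never say how the per-visit CI is to be read. The synopsis is the only text that does, and it reads the CI as a test. Under Protocol 12.5.4 and SAP 5.9 the secondary endpoints support the primary conclusion once the primary is met. A rise in control described as significant on this basis would be cited as corroboration although the entry rule can generate it.

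**Working it through.** **Inputs from the documents.** 216 patients start the assessment period. This is the primary-endpoint sample size; no size or power is given for the goal rates. The figure reproduces with a difference of 4 − 2 = 2 mmHg, SD 10, 90% power and a one-sided 5% paired t-test (n = 216, power 90.1%). Here it serves only as the denominator. The SD of DBP change is 10 mmHg (Protocol 12.2). Entry is SBP 140–179 and/or DBP 90–109 (inclusion criterion 1). Patients continue at Visit 2 if SBP >130 or DBP >80 and they are below Grade 3.

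**Step 1: how many patients at goal exclude 0%?** Lower 95% limits with n = 216:

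| At goal | Exact | Wilson | Wald |
|---|---|---|---|
| 1 | 0.012% | 0.082% | 0 (truncated) |
| 3 | 0.287% | 0.473% | 0 (truncated) |
| 4 | 0.507% | 0.722% | 0.054% |

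The exact limit for 1 patient is 1 − 0.975^(1/216) = 0.012%. The Wald limit for 4 patients is 0.01852 − 1.96 × √(0.01852 × 0.98148/216) = 0.0005. So 1 patient suffices with exact or Wilson limits, and 4 are needed with Wald.

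**Step 2: chance of excluding 0% if the combination is inert.** Let p be the proportion at goal on re-measurement with no drug effect. The documents do not give p. The chance is 1 − (1 − p)^216 for exact limits and P(X ≥ 4), X ~ Bin(216, p), for Wald.

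| p | Exact | Wald |
|---|---|---|
| 0.5% | 66% | 2% |
| 1% | 89% | 17% |
| 2% | 98.7% | 63% |
| 3% | 99.9% | 89% |
| 5% | about 100% | 99.5% |

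A 95% chance needs p = 1.4% (exact) or 3.6% (Wald).

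**Step 3: what might p be?** If the SD of 10 is all within-patient, the per-visit DBP SD is 10/√2 = 7.07. This is an upper bound, because varying drug response would take part of the 10. The remaining inputs are assumptions: per-visit SBP SD 10, underlying mean BP 138/84 to 150/94, between-patient SD 11/7, SBP–DBP correlation 0.6. One million patients per scenario were selected by the Visit 1 and Visit 2 rules and then re-measured with zero effect. Each cell shows p, then the chance with exact limits / Wald limits at n = 216:

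| Mean BP | Per-visit SD 10/7.07 | 8/5 | 6/4 |
|---|---|---|---|
| 138/84 | 6.8%: 100% / 100% | 3.6%: 100% / 96% | 1.7%: 97% / 48% |
| 142/87 | 4.6%: 100% / 99% | 2.3%: 99% / 73% | 1.0%: 88% / 16% |
| 146/90 | 3.0%: 99.9% / 89% | 1.3%: 95% / 33% | 0.5%: 69% / 3% |
| 150/94 | 1.7%: 97.5% / 50% | 0.6%: 75% / 5% | 0.2%: 38% / 0.1% |

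In the 10/7.07 column the simulated SD of DBP change is 9.6 to 9.7, close to the plan's 10. The mean DBP change is only −0.58 to +0.44 mmHg, so the goal rate leaves 0% with almost no movement in the mean.

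**Step 4: sensitivity.** With n = 162 (25% loss after Visit 2, assumed), the 10/7.07 column gives 94% to 100% exact and 29% to 99.6% Wald. Some passages give entry as 140/90 to 179/109, which could be read as requiring both pressures to be raised. At n = 216 that reading gives 88% to 100% exact at 10/7.07 and 10% to 57% exact at 6/4.

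**The case against.** The strongest reply concerns scope. The clause stands only in the synopsis, beside the word descriptively. Protocol section 12 lets the SAP modify the Protocol's plans and requires an amendment only for major changes to the primary endpoint or its analysis. The SAP plans an interval per visit and its table tests nothing. A reader might infer that the planned output will report a significant rise in control; the SAP and its tables do not support that. What remains is that nothing in the SAP withdraws the synopsis reading or replaces it.

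A second reply is that the test has no inflated type I error in the strict sense. If the true rate were 0%, nobody would be at goal and the interval would never exclude 0. That is correct. The fault is one of attribution: rejecting a rate of 0% is not evidence of a drug effect.

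A third is that the interval is still informative. A control rate far above what re-measurement could plausibly give would say something about the combination, though without a control. This also stands, and it is why the rates should be kept and only the significance reading dropped.

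**Conclusion.** The concern holds for the synopsis clause. The 0% reference follows directly from the withdrawal rule and needs no assumption; nor does the finding that 1 patient of 216 (exact or Wilson) or 4 (Wald) would count as significant. The chance of that under an inert combination does rest on assumptions: about 97% to 100% (exact) or 50% to 100% (Wald) with and/or entry, per-visit SD 10/7.07 and the assumed mean BPs.

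Two stronger readings are not supported. A reader might infer that significance is close to guaranteed. The documents give neither the spontaneous control rate nor the CI method, and at per-visit SD 6/4 with and/or entry the chance falls to 38% to 97% (exact) and 0.1% to 48% (Wald). A reader might also take the Visit 2 row of Table 14.2.3.3 as a second faulty comparator, because it uses all consented patients while Visits 3 and 4 use the Efficacy population. No section makes it a comparator, and the table note already states that "The Monotherapy analysis (Visit 2) is performed on the Full Analysis Set".

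The primary analysis is unaffected. This is a wording defect in how secondary and exploratory results are to be read.

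**What to change.** 1. Delete the clause on a significant difference from Week 0 from the synopsis and keep the descriptive analysis.
2. State in SAP 7.3.2 and Table 14.2.3.3 that the Visit 3 and Visit 4 rates are descriptive control rates among patients uncontrolled on monotherapy, with a named CI method such as Clopper-Pearson or Wilson. Naming the method without step 1 would not help, since under either of these a single patient excludes 0.
3. Add a footnote to Table 14.2.3.3 that the Efficacy-population Visit 2 rate is 0% by selection and that no before-after significance claim is made.

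The Visit 2 goal rate in patients who continued their previous drug (Table 14.2.4.3) should not be put in as a substitute reference. It is based on the Full Analysis Set and follows selection at a different threshold (140/90 at Visit 1).

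The cost is one deleted clause, handled under Protocol 12.6, one SAP sentence and one footnote, with no new data. The sponsor gives up a significance statement that the design cannot support.
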